### **Stopping Rule for Necrosis:**

Necrosis will be monitored throughout the trial and accrual to the trial suspended at any time the following stopping criteria are met. Necrosis will be graded according to the CTCAE v4.0 terminology. If evidence develops that more than 20% of patients are expected to develop necrosis (CTCAE v4.0 > grade 3) the treatment will be considered unacceptable. The number of patients who experience necrosis is based upon the number of enrolled patients. The stopping criteria shown in the following table are based on exact lower 95% Blyth-Still-Casella confidence bounds.

> St. Jude Children's Research Hospital IRB NUMBER: Pro00004349

IRB Approval date: IRB APPROVAL DATE: 02/01/2023

Number of Patients	Number of Eligible	Exact 95% Lower
Experiencing Necrosis	Patients	Confidence Bounds
7	≤ 20	≥ 0.201
10	≤ 30	≥ 0.193
13	≤ 40	≥ 0.204
16	≤ 50	≥ 0.211
18	≤ 60	$\geq$ 0.204
20	≤ 70	≥ 0.202
23	≤ 80	≥ 0.211

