## Necrosis

Necrosis will be defined by enhancement of normal tissues as assessed by contrast-enhanced T1-weighted MR imaging, increased signal on T2 and FLAIR imaging, and the imaging parameters of apparent diffusion coefficient, fractional anisotropy, FDG-PET, and MR spectroscopy, when available. The gold standard to diagnose radiation necrosis has been biopsy; however, surgical intervention may increase morbidity, especially when considering the brainstem and cerebellum. Several imaging modalities have been investigated for their ability to diagnose necrosis and distinguish between necrosis and recurrent tumor. We will rely on serial changes, including increasing parenchymal enhancement on postcontrast T1 images and increasing volume of T2-weighted MR imaging signal abnormality and symptoms to grade necrosis according to the CTCAE v4.0. We have found that resolution of necrosis can be a long process during which lesions can show signs of improvement followed by progression in the same or other sites before stabilizing. According to the CTCAE v4.0 terminology, CNS necrosis has five grades: (1) asymptomatic; clinical or diagnostic observations only; intervention not indicated, (2) moderate symptoms; corticosteroids indicated, (3) severe symptoms; medical intervention indicated, (4) life-threatening consequences; urgent intervention indicated, (5) death. We anticipate that the rate of CNS necrosis (CTCAE v4.0 > grade 3) will be greater than 5% and less than 20% when estimated at one year. The lower bound of this estimate is based on our published data for patients treated in the primary setting [6, 137, 296]. The upper bound of this estimate is empiric. Asymptomatic patients with grade 1 necrosis referred for hyperbaric oxygen or other interventions to prevent progression of

> St. Jude Children's Research Hospital IRB NUMBER: Pro00004349

IRB Approval date: IRB APPROVAL DATE: 02/01/2023 imaging findings and the potential development of symptoms will be scored as grade 1 with supportive documentation.

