The one interim analysis, based on the work by Xiong et al, [298] will be conducted when 50% of the expected number of failures (67) for the 90 patients to be treated prospectively (assuming the alternative hypothesis) has been observed (~34 patients have failed). The planned interim analysis will occur at approximately 68% of the expected total "transformed information time," assuming the alternative hypothesis. Accrual will be suspended until all available information has been considered, if the observed nominal p-value is  $\leq 0.0582$ . At the final analysis, one would conclude that the prospective results are inferior to the retrospective results if the p-value is  $\leq 0.10$ . The log-rank comparisons will be stratified by three strata define above and the power should be retained [299]. With this design the actual significance level is 0.1089; the power is 0.7915 and the maximum probability of an interim decision being discordant with a decision that would be made by a final analysis is 0.05 (5%).

While the expected accrual to this trial is considerably greater than our historical experience, we expect that accruing 12 patients per year is realistic. Our current case review for re-irradiation includes approximately two chart review consultations per month. Patients treated to date include those previously irradiated in department or from our region. Based on institutional policy, patients cannot be accepted for treatment at St. Jude in the absence of a clinical protocol. Thus when this trial opens, we will begin to actively recruit patients for the trial. Furthermore, we have offers from a number of centers to collaborate in this effort. If accrual is not meeting expectations by the end of year 2, we will contact these centers to participate.

At the time of amendment #2, the study had been open for 4 years and we accured 53 patients. The accrual rate was approximately 10 patients/year and less than the 15 patients per year target (initial). We extended the accrual time by 3 years to reach the accrual goal and added a collaborative site.

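### The necrosis stopping rule states no time horizon and counts patients with little or no follow-up in its denominator, so it under-reads necrosis while accrual is young

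*Combined protocol and SAP*

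**What the plan says.** The Necrosis part of section 7.0 anticipates that the rate of CNS necrosis of the qualifying grade "will be greater than 5% and less than 20% when estimated at one year". It adds: "The upper bound of this estimate is empiric".

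The stopping rule in section 11.1 uses the same grade definition and the same 20%. It judges the treatment unacceptable "If evidence develops that more than 20% of patients are expected to develop necrosis", with no time window. On timing it says "Necrosis will be monitored throughout the trial and accrual to the trial suspended at any time the following stopping criteria are met". On the denominator it says "The number of patients who experience necrosis is based upon the number of enrolled patients", although the table column counts eligible patients. The counts are 7 for up to 20 patients, then 10 (30), 13 (40), 16 (50), 18 (60), 20 (70) and 23 (80), "based on exact lower 95% Blyth-Still-Casella confidence bounds".

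On pace, section 11.1 says "we expect that accruing 12 patients per year is realistic" and, at amendment 2, "The accrual rate was approximately 10 patients/year". Section 4.4 sets no limit on the time from enrollment to irradiation. No minimum follow-up or time-to-event estimate is given for necrosis.

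**The concern.** An exact binomial bound for x events in n patients is valid when each of the n has had the full opportunity to show the event. Here the count is events so far, and n includes patients enrolled last week and patients not yet irradiated. The crude proportion is therefore below the rate that the 20% describes, and the gap is widest when n is small, which is when early suspension would protect most patients.

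The rows also move on with enrollment. If necrosis in one of the first 20 patients appears after the 21st has enrolled, it is judged against 10 of 30 and no longer against 7 of 20.

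This matters because monitoring for excessive necrosis is part of the primary objective, and section 9.1 excludes necrosis from the events treated as serious or unexpected. The table is thus the main quantitative safeguard.

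**Working it through.** **1. The plan's own bounds.** The lower limit of the two-sided 90% Blyth-Still-Casella interval (one-sided 95%) gives 0.201, 0.193, 0.204, 0.212, 0.204, 0.202 and 0.211 for the seven rows. The printed values are 0.201, 0.193, 0.204, 0.211, 0.204, 0.202 and 0.211, so all agree within 0.001. The two-sided 95% version does not match. The table is thus a simple binomial one with no allowance for incomplete follow-up.

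**2. Share of first-year events visible at n enrolled.** Assume steady accrual of a patients per year, irradiation at entry, and onset uniform over the first year. The latest a patients have on average shown half of their first-year events, so

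visible share = 1 − 0.5 × a / n.

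- n = 20: a = 10 gives 0.75, a = 11 gives 0.725, a = 12 gives 0.70.
- a = 12: n = 40 gives 0.85, n = 80 gives 0.925.
- Lag of 0.25 year to irradiation (assumed), a = 12, n = 20: 1 − (0.5 + 0.25) × 12/20 = 0.55.
- Onset uniform over 8 months, a = 11, n = 20: 1 − 0.5 × (11 × 8/12)/20 = 0.82.

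At a true one-year rate of 30%, with 20 enrolled and a = 12, the expected visible count is 20 × 0.30 × 0.70 = 4.2. With full follow-up it would be 6.0. The boundary is 7.

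**3. Chance of suspension.** Simulation of 90 patients at 11 per year, onset uniform over year 1, no later necrosis, and no death or progression. The printed rule is checked continuously during accrual. The alternative applies each row to the first n irradiated patients and keeps it open until all n have one year of follow-up.

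| True one-year rate | Printed rule | First n, printed counts | First n, each count + 1 |
|---|---|---|---|
| 20% | 6% | 15% | 7% |
| 25% | 26–27% | 44% | 31% |
| 30% | 60–62% | 77% | 67% |
| 30%, 3-month lag | 50% | 76% | not run |

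A separate run at 12 per year, using only patients with a full year of follow-up as the denominator, also gave 60% against 77% at a 30% rate. A second run of the last column gave 7.5%, 30% and 64%, so these figures are good to within about three points.

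**The case against.** Four objections have force.

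**Unequal error rates.** Comparing 60% with 77% flatters the alternative, which also suspends more often at exactly 20% (15% against 6%). With each count raised by one, the error rates are close, and the gain falls to 31% against 26% at a 25% rate and 67% against 62% at 30%. This stands, and the size must be stated that way.

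**Onset may be faster.** Section 2.1 says brainstem necrosis after a first course usually appears less than 8 months after the start of irradiation. On that timing about 82% of events are visible at n = 20, and the printed rule suspends about 68% of trials at a 30% rate. A lag to irradiation works the other way. The documents give no onset distribution after re-irradiation.

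**Much of accrual has passed.** By amendment 2, 53 patients had been accrued, so the rows where the under-reading is largest are behind the trial. The later rows remain, and the early ones can be re-read by entry order.

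**A one-year limit is not stated.** Section 7.0 gives an anticipated rate and does not set a limit; only section 11.1 speaks of unacceptability, and it has no window. A reader might infer that late necrosis causes false stops at an acceptable one-year rate. The documents do not support that. Section 11.1 can be read as limiting cumulative necrosis. With 18% in year 1 plus an assumed 3% per year later, five-year necrosis is 1 − 0.82 × exp(−0.12) = 27%, and suspension would be what that reading asks for. The contrast also depends on assumed late rates. If recording of necrosis ends at progression (an assumption; section 8.1 makes progression an off-study criterion) and the plan's hazard of 0.233 is used, the printed and first-n rules suspend 9% and 10%. For 15% plus 4% per year they suspend 4% and 3%.

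**Conclusion.** The concern holds for early under-reading and for the missing horizon. The rule uses bounds that require complete observation on a denominator that includes patients with little or none, and section 11.1 does not say over what period the 20% applies. If cumulative necrosis is meant, the early under-reading is greater, because more follow-up is missing, so a horizon is needed on either reading.

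The size is moderate. About 18% to 30% of first-year events are unseen at 20 enrolled without a lag, and 45% with a 3-month lag at 12 per year. At a 30% rate, detection is about 60% (50% with the lag) against about 77% with unchanged counts, but only about five points better at a similar error rate. These figures rest on assumed onset timing, steady accrual, and no death or progression. No conclusion about false stops from late necrosis is drawn.

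**What to change.** - State one horizon in the stopping rule, reconciled with section 7.0, and count it from the start of re-irradiation.
- Use irradiated eligible patients as the denominator, which also settles the mismatch between enrolled in the text and eligible in the table.
- Apply each row to the first n such patients in entry order, keep the row open until all n reach the horizon, and act as soon as the count is reached.
- State the chance of suspension at a true 20% rate and at higher rates. With the printed counts it is about 15% at 20%, and with each count raised by one about 7%, against about 6% now. The sponsor should choose the counts knowing this trade-off.
- State whether necrosis after the horizon also counts towards suspension, and tabulate it in any case.

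The cost is a wording change, bookkeeping by entry order, and a short recalculation. No new visits or data are needed. If the printed counts are kept, the price is the higher chance of suspending at a true 20%.

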#### 3.3 Recruitment

The statistical design of this trial requires that 90 eligible patients be enrolled over a 9 year period. Accounting for ineligible patients, which are expected to be at most 10%, the total number of patients to be accrued to this study may be 99. We expect to enroll about 12 patients per year for approximately 9 years. The study will enroll patients with ependymoma and progressive disease. There is no exclusion to enrollment based on the time interval between initial tumor progression and enrollment. In the event that the accrual of patients is slower than expected, we will consider collaborating with other centers that specialize in the treatment of ependymoma. Patients with a prior history of radiosurgery may be excluded from protocol enrollment if the principal investigator or his designee determines that the risk of injury associated with fractionated retreatment is excessive.

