#### 4.0 TREATMENT AND PLAN STRATIFICATION

#### 4.1 Overview

Patients will be enrolled on this protocol at St. Jude Children's Research Hospital (SJCRH) if they meet the eligibility criteria outlined in section 3.0. Patients may be enrolled before or after surgery performed at the time of recurrence. Enrollment prior to surgery is preferred to prospectively obtain peri-operative information about surgical morbidity and to facilitate the acquisition of tissue for biology studies. This protocol allows for co-enrollment on other protocols for recurrent ependymoma including those that might administer chemotherapy after irradiation. Chemotherapy concurrent with radiation therapy will not be allowed. Patients will be jointly evaluated by treatment teams representing neuro-oncology, radiation oncology and neurosurgery.

In the event that collaborative sites are allowed to join this trial, SJCRH will not be financially responsible for the cost of surgery, radiation therapy or follow-up for patients enrolled at collaborative sites. All patients are expected to undergo clinically indicated follow-up measures at the enrolling institution or at their routine point of care. Collaborative sites are expected to perform the research outlined in the protocol unless otherwise specified. The PI and protocol team at SJCRH will establish appropriate and legal (HIPAA) compliant communication with the enrolling institutions and the routine point of care for each patient.

Patients will be considered for enrollment if they have progressive disease after prior therapy that included surgery and focal irradiation with or without chemotherapy. There is no limit regarding the time interval from initial treatment failure to enrollment on this protocol which means that patients may choose other forms of therapy prior to enrollment on this protocol. Multiple episodes of progression will be allowed. The most common enrollment scenario will be the

Rev. 3.2 dated: 1/19/2023 IRB Approval date: St. Jude Children's Research Hospital IRB NUMBER: Pro00004349

patient who has been diagnosed with asymptomatic recurrence noted on surveillance neuroimaging. This patient will be consented for the study and will undergo pre-operative evaluations. Post-operatively, the studies necessary for treatment planning and to assess the impact of resection will be performed or repeated.

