## 10.2 Study Monitoring

# High Risk 3 (HR-3) – Phase II or Phase III Therapeutic Studies with an IND or IDE

The Eligibility Coordinators will verify 100% of the informed consent documentation on all participants and verify 100% of St. Jude participants' eligibility status within 10 working days of the completion of enrollment.

The study team will meet at appropriate intervals to review case histories or quality summaries on participants.

The Clinical Research Monitor will assess protocol and regulatory compliance as well as the accuracy and completeness of all data points for the first 2 participants then 15% of study enrollees every 6 months. Accrual will be tracked continuously for studies that have strata. All SAE reports will be monitored for type, grade, attribution, duration, timeliness and appropriateness on all study participants *semi-annually*.

The monitor will also verify 100% of all data points on the first 2 participants and on 15% of cases thereafter. Protocol compliance monitoring will include participant status, eligibility, the informed consent process, demographics, staging, study objectives, subgroup assignment, treatments, evaluations, responses, participant protocol status, off-study, and off-therapy criteria. The Monitor will generate a formal report which is shared with the Principal Investigator (PI), study team and the Internal Monitoring Committee (IMC).

Monitoring may be conducted more frequently if deemed necessary by the CPDMO or the IMC.

Continuing reviews by the IRB and CT-SRC will occur at least annually. In addition, SAE reports in TRACKS are reviewed in a timely manner by the IRB/OHSP.

IRB APPROVAL DATE: 02/01/2023

St. Jude collaborating study sites will be monitored on-site by a representative of St. Jude at intervals specified in the Data and Safety Monitoring Plan. International collaborators will be monitored according to the study-specific monitoring plan.

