#### 11.0 STATISTICAL CONSIDERATIONS

The primary objective of this protocol is to prospectively estimate the PFS and OS distributions of children and young adults after a second course of irradiation and to demonstrate that many of these patients may be safely salvaged, if additional surgery and radiation therapy are administered. PFS and OS distributions will be measured from the initiation of re-irradiation. The historical data discussed below are retrospective and without correlative neuropsychological and quality of life information; thus, the data are not sufficiently convincing for most investigators.

To conduct this trial, we expect that a high percentage of patients will have received chemotherapy post progression and prior to registering on this trial. The primary objective will be assessed without regard to whether patients did or did not receive prior chemotherapy. However, the potential association of primary outcome with specific chemotherapy given prior to re-irradiation will be explored (exploratory objective 1.3.4).

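### The necrosis stopping rule names two denominators, neither of which requires that re-irradiation has started, and prints no cut-off for eligible patients 81 to 90

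*Combined protocol and SAP*

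**What the plan says.** The rule sits in Section 11.1 under Stopping Rule for Necrosis. Accrual is suspended when necrosis above the stated grade reaches a tabulated count, and treatment is judged unacceptable if the evidence points to a rate over 20%. On the denominator the text says "The number of patients who experience necrosis is based upon the number of enrolled patients". The table column directly below reads "Number of Eligible" patients. Its rows run from 7 events among at most 20 patients to 23 among at most 80. Monitoring is to last for the whole trial.

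Section 3.3 distinguishes the two groups: "The statistical design of this trial requires that 90 eligible patients be enrolled over a 9 year period". It then allows for ineligible patients, put at no more than 10%, to reach a total of 99.

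Elsewhere the plan works from treatment. Section 11.0 says "PFS and OS distributions will be measured from the initiation of re-irradiation", and the PFS interim analysis in Section 11.1 counts failures "for the 90 patients to be treated prospectively".

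Enrolment can come well before treatment. Section 4.1 says "Enrollment prior to surgery is preferred", and it removes patients left with devastating surgical morbidity. Section 4.4 sets no limit on the time from enrolment to irradiation. Section 4.2 adds that patients treated elsewhere will often already have had surgery, which shortens the gap for them.

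**The concern.** The rule is meant to judge necrosis after a second course of radiation. A patient who has not had that course cannot have the event, yet enters either denominator as necrosis-free. Reading the rule as *eligible* does not remove the problem. The eligibility criteria do not mention starting treatment, and Section 10.2 verifies "eligibility status within 10 working days of the completion of enrollment", which does not screen out a patient removed later.

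Three things follow. Two people can apply the rule to the same data and disagree near a cut-off. Its sensitivity depends on a share of unexposed patients that nobody knows in advance. For the last ten planned eligible patients there is a principle but no printed number.

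This matters because watching for excessive CNS necrosis is part of the primary objective and this is the only boundary that counts it. Section 9.1.2.1 also lists necrosis among events not treated as serious or unexpected, so expedited reporting is a weak second safeguard.

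**Working it through.** **Inputs.** Cut-offs and the 20% limit: Stopping Rule for Necrosis. Planned numbers (90 eligible, 99 in total, about 12 a year): Section 3.3. The documents do not give the time from enrolment to radiation, the onset distribution or the share never irradiated. These are assumed below and varied.

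**1. The plan's own table.** The printed bounds match the lower ends of two-sided 90% Blyth-Still-Casella intervals:

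| Events / patients | Printed | Recomputed |
|---|---|---|
| 7/20 | 0.201 | 0.201 |
| 10/30 | 0.193 | 0.193 |
| 13/40 | 0.204 | 0.204 |
| 16/50 | 0.211 | 0.212 |
| 18/60 | 0.204 | 0.204 |
| 20/70 | 0.202 | 0.202 |
| 23/80 | 0.211 | 0.211 |

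The two-sided 95% version and the one-sided Clopper-Pearson bound do not match every row (Clopper-Pearson gives 0.177 for 7/20 and 0.198 for 20/70). The matching method gives 0.191 for 24/90 and 0.201 for 25/90, so 25 is the table's natural next entry.

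**2. Size of the gaps.** Enrolled versus eligible: 99 - 90 = 9 patients at most. No printed cut-off: 90 - 80 = 10 patients (10/90 = 11%) if the denominator is eligible patients, or 99 - 80 = 19 (19/99 = 19%) if it is enrolled patients.

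**3. How unexposed patients shift a cut-off.** If a share f of the n counted patients is never irradiated, reaching r events needs an observed rate of r / (n(1 - f)) among the irradiated. With f = 0.10, 23/80 = 0.288 becomes 23/72 = 0.319, and 7/20 = 0.350 becomes 7/18 = 0.389.

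**4. Crossing probability if necrosis were known at once.** This is an exact binomial recursion, checking after every patient. At a true 30% the existing table is crossed by patient 80 with probability 0.77. A cut-off of 25 for patients 81 to 90 raises that to 0.81. If 10% are not irradiated, 0.77 falls to 0.58.

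**5. Crossing probability with timing.** Simulation of 90 eligible patients at 12 a year, radiation 2 months after enrolment, onset uniform over 3 to 12 months after radiation starts, and the table applied at each event until the last enrolment. Here enrolled and eligible coincide.

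| | As written | Irradiated denominator | Irradiated plus 25/90 |
|---|---|---|---|
| True 30%, all irradiated | 46% | 53-54% | 57% |
| True 30%, 5% never irradiated | 36-37% | | 55-56% |
| True 30%, 10% never irradiated | 27% | | 53-55% |
| True 20%, all irradiated | 3% | 4-5% | 4-5% |

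Varying the timing at a true 30%, all irradiated (same column order):
- 1-month lag: 50 / 53 / 58%
- 3-month lag: 42 / 53 / 56%
- 10 patients a year: 52 / 58 / 61%
- onset 1 to 8 months: 57 / 63 / 66%; false suspension at a true 20% then goes from about 5.5% to 7.8%

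If 9 of 99 accrued patients are ineligible and never irradiated (an assumed worst case), detection at a true 30% is 29% counting enrolled, 49% counting eligible, 55% counting irradiated, and 59% with the extra row.

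**The case against.** The strongest reply concerns weight. If everyone is irradiated promptly, the gain is modest, and looser cut-offs on enrolled patients would match it (59% detection at 4.5% false suspension, against 57.5% at 4.2%). That stands. Those looser cut-offs do not hold up when patients go untreated, however: they fall to 48% or 37% with 5% or 10% never irradiated. Those shares are assumptions, and Section 4.1 removes only the most severely injured patients. The large contrasts should therefore be read as conditional.

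A second reply is that most of the lost sensitivity comes from short follow-up. Instant ascertainment would give 77% against 46% as written, a gap of 31 points, and changing the denominator recovers about 7 (46% to 53%). A patient one day into radiation would still count as necrosis-free, although Section 7.0 frames the expected rate at one year. That stands too.

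A reader might make three stronger inferences that the documents do not support:
- *The rule is silent after patient 80.* The 20% criterion and monitoring throughout the trial still apply; what is missing is a count, which the named method can supply.
- *The method is unstated.* The sentence introducing the table names lower 95% Blyth-Still-Casella bounds; only the correspondence with a two-sided 90% interval is left unsaid.
- *The 10/30 row breaks the rule.* No sentence requires every printed bound to exceed 0.20, and the 0.193 is openly shown.

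Enrolled and eligible can also be read together as eligible patients who enrolled. That narrows the wording conflict but still does not require exposure.

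**Conclusion.** The point holds as a specification defect. The text and table name different denominators, neither requires that re-irradiation has started, and eligible patients 81 to 90 have no printed cut-off. The table's arithmetic is sound.

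The effect is modest if all patients are irradiated (about 46% to 57% detection at a true 30%). It becomes substantial only if some never are: about 36% or 27% as written at an assumed 5% or 10%, against 53-56% after the change. All these figures rest on the assumed lag, onset and accrual. The main benefit is that the rule's sensitivity no longer depends on an unknown unexposed share. It should be fixed because the rule serves the primary objective and the change is small. It should not be presented as a cure for immature follow-up.

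**What to change.** Use one denominator in both places:
- Text: *Necrosis counts are judged against the number of eligible patients who have started re-irradiation.*
- Column header: *Eligible patients who have started re-irradiation.*
- New last row: 25 events / ≤ 90 patients / ≥ 0.201.

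Leave the existing cut-offs, the 20% limit and the grade as they are.

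Two editorial notes: state that the printed bounds correspond to lower ends of two-sided 90% Blyth-Still-Casella intervals, and have the sponsor confirm the 10/30 row, whose bound of 0.193 is below 0.20.

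No new data are needed, because the first day of radiation is already time zero for follow-up (Section 6.9.2) and PFS runs from it. The statistical cost is a rise in false suspension at a true 20% rate from about 3% to 5%, or from 5.5% to 7.8% if onset is at 1 to 8 months.
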